6. ENDPOINTS AND COVARIATES

6.1. Safety Endpoint

- Safety specification: Interstitial lung disease

Events to be handled as interstitial lung disease will be specified separately.

6.2. Efficacy Endpoint

- Best overall response (according to the "Response Evaluation Criteria in Solid Tumors Guidelines - Revised Version 1.1")

6.3. Other Endpoints

- Confirmation of survival status

6.4. Covariates

The known risk factors for drug-induced lung injury include age of ≥ 60 years, past pulmonary lesion (especially interstitial pneumonia), post-lung surgery patients, decreased respiratory functions, oxygen therapy, irradiation to the lung, and presence of renal disorder.

7. HANDLING OF MISSING DATA

If the seriousness, causal relationship, action taken, and outcome of interstitial lung disease are missing, the data will be handled as “unknown” for tabulation.

Any missing efficacy endpoint will not be imputed.

The strategy for handling data with uncompleted cleaning is as follows.

- Item of missing data: The item will be handled as missing (category of categorical variables is “unknown”) for both tabulation and listing.
- Item of inconsistent data: The item will be handled as missing for both tabulation and listing. However, a listing of data handling will be prepared separately.
- No signature: Any entry in a case report form without the signature of a contracted physician (including a case report form with the signature of an uncontracted physician only) will be handled as missing for both tabulation and listing.

8. STATISTICAL METHODS AND STATISTICAL ANALYSIS

8.1. Statistical Methods

8.1.1. Analysis of Continuous Data

Summary statistics (number of patients, mean, standard deviation, median, maximum, minimum) will be calculated.

8.1.2. Analysis of Categorical Data

The frequency and proportion of data will be calculated for each category.

8.1.3. Analysis of Binary Data

The frequency and proportion of data will be calculated. When the confidence interval of the proportion is calculated, the two-sided 95% confidence interval (exact method) will be presented.

8.1.4. Analysis of Period Data (Time to Event Onset)

The median, first quartile, and third quartile will be calculated by the Kaplan-Meier method. The 95% confidence interval will be calculated using the Brookmeyer and Crowley method. In addition, Kaplan-Meier plots will be prepared.

8.2. Statistical Analysis

8.2.1. Overview of Patients

8.2.1.1. Patient Disposition

For registered patients, the number of registered patients, the number of patients completing the study, the number of patients in the safety analysis set, and the number of patients in the efficacy analysis set will be tabulated. In addition, the number of CRF-uncollected patients, the number of patients excluded from the safety analysis set, and the number of patients excluded from the efficacy analysis set, and the number of patients by reason for exclusion will be tabulated.

8.2.1.2. List of Discontinuations and Dropouts

For the safety analysis set and the efficacy analysis set, the number and proportion of discontinuations will be tabulated. In addition, the number and proportion of patients by reason for discontinuation (insufficient clinical efficacy, adverse event, death, no revisit, transfer to other hospital/department, other) will be tabulated.

8.2.1.3. Listing of Excluded Patients by Patient

A listing of patients excluded from the safety analysis and patients excluded from the efficacy analysis by reason for exclusion will be prepared.

8.2.2. Patient Characteristics and History of Treatment

8.2.2.1. Patient Characteristics

For the safety analysis set and the efficacy analysis set, the following patient characteristics will be tabulated as described in Section 8.1.

- Gender (categorical [male, female])
- Age (continuous, categorical [<15 years, ≥15 to <65 years, ≥65 years])
- Body weight (continuous, categorical [<50 kg, ≥50 to <70 kg, ≥70 kg])
- BMI (continuous, categorical [<18.5 kg/m², ≥18.5 to <25.0 kg/m², ≥25.0 kg/m²])
- Height (continuous)
- Disease name (categorical [EGFR mutation-positive inoperable or recurrent NSCLC, other])
- Time from the date of initial diagnosis of NSCLC to the start of administration of this drug (continuous, categorical [<6 months, ≥6 to <12 months, ≥12 to <18 months, ≥18 to <24 months, ≥24 months])
- EGFR mutation test results (categorical [positive, negative, equivocal, not performed])

If there is more than one test result, one result will be adopted in the order of positive, equivocal, and negative.

- EGFR mutation test method showing a positive test result (categorical [therascreen® EGFR mutation detection kit RGQ “Qiagen,” cobas® EGFR mutation detection kit v2.0, other, no test method showing a positive test result, test not performed])
- Target lesion (categorical [absent, present])
- T classification (categorical [TX, T0, Tis, T1mi, T1a, T1b, T1c, T2a, T2b, T3, T4])
- N classification (categorical [NX, N0, N1, N2, N3])
- M classification (categorical [M0, M1a, M1b, M1c])
- Metastatic site (categorical [absent, liver, lymph node, bone marrow, bone, brain, adrenal gland, skin, peritoneum, other])
- Histopathological diagnosis (categorical [replacement adenocarcinoma, acinar adenocarcinoma, papillary adenocarcinoma, micropapillary adenocarcinoma, adenocarcinoma in situ, solid adenocarcinoma, special type adenocarcinoma, minimally invasive adenocarcinoma, unclassified adenocarcinoma, atypical adenomatous hyperplasia, squamous cell carcinoma, large cell carcinoma, adenosquamous cell carcinoma, other, not performed])

- ECOG PS (categorical [0, 1, 2, 3, 4, not performed])
- Smoking history (categorical [absent (non-smoker), past (ex-smoker), present (smoker), unknown])
- Brinkman index (continuous, categorical [0, >0 to <200, ≥200 to <400, ≥400])
- History of occupational/environmental exposure to asbestos, pneumoconiosis, etc. (categorical [absent, present, unknown])
- Oxygen administration for treatment of respiratory disease (categorical [absent, present, unknown])
- Number of prior therapies for NSCLC (including EGFR-TKI) (categorical [0, 1, 2, 3, 4, ≥5])
- History of drug therapy for NSCLC (categorical [absent, present])
- History of drug therapy for NSCLC (EGFR-TKI) (categorical [absent, present])
- History of previous drug therapy for NSCLC
 - EGFR-TKI (1) (categorical [absent, present])
 - EGFR-TKI (2) (categorical [absent, afatinib, gefitinib, erlotinib, osimertinib])
 - Chemotherapy (categorical [absent, present])
 - History of other specific drug therapy (by therapeutic class [subclass]) (categorical [absent, present])
- Past illness (categorical [absent, present])
- Past illness: Interstitial lung disease (categorical [absent, present])
- Past illness: Lung lesion (excluding interstitial lung disease) or decreased respiratory function (categorical [absent, present])

The disease name (PT) corresponding to lung lesion (excluding interstitial lung disease) or decreased respiratory function should be asthma/bronchospasm (SMQ narrow), respiratory failure (SMQ narrow), or “chronic obstructive pulmonary disease.”

- Complication: (categorical [absent, present])
- Complication: Interstitial lung disease (categorical [absent, present])
- Complication: Lung lesion (excluding interstitial lung disease) or decreased respiratory function (categorical [absent, present])
- Complication: Hepatic impairment (categorical [absent, present])
- Complication: Renal impairment (categorical [absent, present])

For disease names (PT) corresponding to hepatic/renal impairment, the latest “procedure for extraction of hepatic/renal impairment” will be followed.

- History of surgery for NSCLC (categorical [absent, present])
- Prior radiotherapy for NSCLC (categorical [absent, present])

8.2.2.2. Disease History

For the safety analysis set, the numbers and proportions of patients with past illness and complications will be tabulated by system organ class (SOC) and preferred term (PT).

8.2.2.3. Administration Status of This Drug

For the safety analysis set, the administration status of this drug will be tabulated for the following:

- Period of administration (≤ 13 weeks, >13 to ≤ 26 weeks, >26 to ≤ 39 weeks, >39 to ≤ 52 weeks, >52 weeks [ongoing])
- Mean daily dose (unit: mg/day)
- Reason for change/interruption (adverse event, other)

The period of administration is defined as the period from the first date of administration to the last date of confirmation of administration in this study, including the non-treatment period. The mean daily dose will be calculated using the following formula:

$$\text{MDD (mg/day)} = \text{aCD (mg)} / \text{DR (days)}.$$

Here, MDD is the mean daily dose, aCD is the total dose during the administration period excluding the non-treatment period, and DR is the number of days of administration excluding the non-treatment period.

8.2.3. Safety Analysis

The analyses described in this section will be performed on the safety analysis set unless other analysis sets are specified. Analyses, other than those to be performed only on the safety analysis set consisting of consented patients in Section 8.2.3.2, will be performed on the safety analysis set consisting of consented patients as necessary.

Adverse reactions and adverse events occurring between the start date of administration of this drug and the end date of the observation period (or 28 days after the day of discontinuation of administration) will be summarized in listings. All events reported in this study will be included in the listings. For the safety tabulations and analyses (Section 8.2.3.1, Section 8.2.3.2, and Section 8.2.3.3) among the safety analyses in this section, the occurrence of interstitial lung disease will be determined based on the investigator’s assessment.

8.2.3.1. Adverse Reactions**8.2.3.1.1. All Adverse Reactions**

The number and proportion of patients with adverse reactions will be tabulated by SOC and PT.

8.2.3.1.2. Serious Adverse Reactions

The number and proportion of patients with serious adverse reactions will be tabulated by SOC and PT.

8.2.3.1.3. Status of Occurrence of Adverse Reactions in Patients Excluded from the Safety Analysis Set

For patients excluded from the safety analysis set, the number of patients with adverse reactions will be tabulated by SOC and PT.

8.2.3.2. Adverse Events

For the safety analysis set consisting of consented patients, the number and proportion of patients with adverse events will be tabulated by seriousness for each SOC and PT. If the same adverse reaction (of the same PT) occurs more than once in the same patient and both serious and non-serious events are reported, the event will be regarded as serious.

For the safety analysis set consisting of consented patients, the number and proportion of patients with serious adverse events of CTCAE Grade 5 will be tabulated.

8.2.3.3. Other Endpoints**8.2.3.3.1. Pregnancy**

For female patients in the safety analysis set, the presence or absence of pregnancy during the observation period of this study will be tabulated.

8.2.3.3.2. Laboratory Test Values

A listing of laboratory test values will be prepared.

8.2.3.3.3. Survival

The numbers and proportions of patients surviving or death on the end date of the observation period will be calculated. In addition, the number and proportion of patients will be calculated by reason for death.

Survival time will be summarized using the Kaplan-Meier method. Patients surviving at the end of the observation period will be censored at the end date of the observation period.

8.2.3.4. Subgroup Analysis

For each of the factors specified in Section 5.4, the number and proportion of patients experiencing interstitial lung disease will be tabulated.

8.2.3.5. Exploratory Analysis

Additional analysis may be performed as necessary. Any exploratory analysis will be reported only when providing results giving important interpretation.

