**STUDY INFORMATION**

Title	Special investigation for VIZIMPRO Tablets
Protocol number	A7471048
Protocol version identifier	Amended 5
Date	18 July 2024
Active substance	Dacomitinib hydrate
Medicinal product	VIZIMPRO Tablets 15 mg/VIZIMPRO Tablets 45 mg
Research question and objectives	To investigate risk factors for interstitial lung disease (ILD) in patients with epidermal growth factor (EGFR) receptor mutation-positive inoperable or recurrent non-small cell lung cancer (NSCLC) under post-marketing actual status of use of VIZIMPRO
Country of study	Japan
Author	PPD

090177e1a1853d10\Final\Final On: 30-Aug-2024 07:48 (GMT)

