1. AMENDMENTS FROM THE PREVIOUS VERSION

Version/ Date/ Author(s)/ Status of Study	Summary of Changes/Comments
1.0 02-SEP-2019 PPD Before Enrollment	First version
2.0 24-APR-2025 PPD Ongoing	
2.1. Study Design
 
 ▪ In association with the protocol amendment, the last days of the investigation period and registration period were changed. 
2.2. Study Objectives
 
 ▪ In association with the termination of the study before the target sample size was reached, explanation about the background and the revision of the evaluation method for the risk of developing interstitial lung disease was added. 
5.3. Other Analysis Sets
 
 ▪ The safety analysis set consisting of consented patients and the efficacy analysis set consisting of consented patients were added. 
5.4. Subgroups
 
 ▪ In association with the revision of the evaluation method for the risk of developing interstitial lung disease, the patient characteristics and factors used for subgroup analyses were limited to the specific backgrounds described in the re-examination application. 
6.4. Covariates
 
 ▪ The description about the evaluation method for the risk of developing interstitial lung disease was deleted. 
8.1.3. Analysis of Binary Data
 
 ▪ In association with the revision of the evaluation method for the risk of developing interstitial lung disease, the description about the calculation of risk ratios was deleted. 
8.2.2.1. Patient Characteristics
 
 ▪ The tabulation items related to mutation test results were changed. ▪ In association with the revision of the evaluation method for the risk of developing interstitial lung disease, the tabulation items were changed to those corresponding to the patient characteristics used for subgroup analyses. ▪ Disease history and treatment history considered to affect the onset of interstitial lung disease were added. 
8.2.2.2. Disease History
 
 ▪ The section itself was added. 
8.2.2.3. Administration Status of This Drug
 
 ▪ In association with the addition of Section 8.2.2.2 “Disease History,” the section number was changed from Section 8.2.2.2 to Section 8.2.2.3. 
8.2.3. Safety Analysis
 
 ▪ The safety analysis set consisting of consented patients was added to the analysis sets. ▪ The description about the evaluation method for the risk of developing interstitial lung disease was deleted.

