2.2. Study Objectives

This study investigates the following in patients with EGFR mutation-positive inoperable or recurrent NSCLC under post-marketing actual status of use of this drug because interstitial lung disease (ILD) was observed in clinical studies of this drug and the incidence was high in Japanese patients, and ILD has also been observed with other EGFR tyrosine kinase inhibitors and it is considered as an adverse event requiring special attention.

The end of the registration period of this study was March 31, 2025. However, 40 patients were registered until that time, and the registration in this study was terminated before the target sample size of 799 patients (888 patients to be registered) was reached. As a result, the initially planned analyses to investigate risk factors are considered to be less significant. Thus, instead of performing these analyses, risk factors will be evaluated to the extent possible based on the information such as patient background of the patients developing interstitial lung disease.

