4. HYPOTHESES AND DECISION RULES

This study is not a confirmatory investigation. Therefore, any test will be considered as exploratory.

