5.4. Subgroups

Subgroup analyses of safety will be performed for the following patient characteristics:

- Age group [<15 years, ≥ 15 to <65 years, ≥ 65 years]

- Complication: Hepatic impairment [absent, present]
- Complication: Renal impairment [absent, present]

Subgroup analyses of safety will be performed for the following other factor:

- Pregnancy status (female only) [absent, present]

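### SAP 8.2.3.5 lets the result decide whether an additional analysis is reported, and five of the seven known lung-injury risk factors in SAP 6.4 have no interstitial lung disease table outside that rule

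*SAP*

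**What the plan says.** The protocol's stated aim is "To investigate risk factors for interstitial lung disease (ILD) in patients with epidermal growth factor (EGFR) receptor mutation-positive inoperable or recurrent non-small cell lung cancer". Protocol 8.7 says that ILD will be tabulated by risk-factor subgroup.

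SAP version 2.0 (24 April 2025) was written after registration closed with 40 patients against a target of 799 for analysis (888 to be registered). Its amendment log records that "the description about the calculation of risk ratios was deleted", and SAP 2.2 gives the replacement: "instead of performing these analyses, risk factors will be evaluated to the extent possible based on the information such as patient background" of the patients who develop ILD.

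The one ILD-by-factor output left in the SAP's methods is in 8.2.3.4: "For each of the factors specified in Section 5.4, the number and proportion of patients experiencing interstitial lung disease will be tabulated". Those factors are age group (cut at 15 and 65), hepatic impairment, renal impairment and pregnancy status. SAP 6.4 separately names seven known risk factors for drug-induced lung injury, without attaching an analysis to them.

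SAP 8.2.3.5 then permits further analyses as needed and adds: "Any exploratory analysis will be reported only when providing results giving important interpretation". SAP 4 says that "any test will be considered as exploratory".

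**The concern.** A rule that looks at the result before deciding whether to report it hides the denominator of the search. A reader who sees one background factor described as associated with ILD cannot tell whether it was the only factor examined or the one kept out of several. Calling the work exploratory does not repair this, because exploratory findings can be weighed only if the extent of the exploration is known.

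The clause matters more here than in most plans. The risk-ratio analysis is gone, and most of the lung-specific factors that the SAP itself calls known risks have no specified ILD table. A look at ILD by those factors would be additional work, which is what the clause covers. Under Protocol 13 the results feed a review of ILD risk minimisation in the risk management plan, so a factor that was examined and showed nothing is information that review should have.

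**Working it through.** The clause has no figure of its own to reproduce. The planning figure only sets the scale. With ILD rates of 5.9% and 11.8%, a low:high ratio of 1:3, two-sided 15% and 80% power (Protocol 8.5.2), a Wald test on the log relative risk gives

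N = 4 × (1.4395 + 0.8416)² × [0.941/0.059 + 0.882/(3 × 0.118)] / (ln 2)² = 798.9, so 799; and 799/0.90 = 887.8, so 888.

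Both stated figures reproduce. The documents give no ILD count for the 40 registered patients. If all 40 were analysed at the planning rates, 40 × 0.059 = 2.4 cases would be expected, or 40 × (0.25 × 0.059 + 0.75 × 0.118) = 4.1 at the planned mix. Any risk-factor evaluation will therefore be a description of a handful of cases.

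The main check is to set the SAP's sections side by side.

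| Known risk factor (SAP 6.4) | ILD table (SAP 5.4, 8.2.3.4) | Background table, whole analysis set (SAP 8.2.2.1) |
|---|---|---|
| Age 60 or over | Age, but cut at 65 | Age, continuous and cut at 65 |
| Past pulmonary lesion | None | Past ILD; other lung lesion or decreased function, combined |
| Lung surgery | None | Surgery for NSCLC, yes/no |
| Decreased respiratory function | None | Combined with other lung lesion |
| Oxygen therapy | None | Oxygen for respiratory disease |
| Lung irradiation | None | Radiotherapy for NSCLC, yes/no |
| Renal disorder | Renal impairment | Renal impairment |

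1. One factor of seven matches directly, one matches with a different cut, and five have no ILD table.
2. The background tables cover the whole analysis set and are not split by ILD, so they compare nothing.
3. SAP 3 commits to performing every analysis specified in the plan. That protects the 8.2.3.4 tables. It does not protect an ILD comparison on the five factors, because none is specified.
4. The evaluation in SAP 2.2 has no method or output in SAP 8. If it goes beyond describing cases and compares ILD by one of the five factors, nothing in the plan covers that comparison except 8.2.3.5.
5. The inputs are collected: disease history and oxygen administration (Protocol 8.3.1), surgery with its site (8.3.3), radiotherapy with its site (8.3.4), and birth year.

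**The case against.** The best defence is that the clause covers only work beyond the plan. The ILD tables for the SAP 5.4 factors carry no condition on the result, and the adverse reaction tables and the listing of patients with adverse reactions (SAP 9) are fixed. The case-background evaluation in SAP 2.2 stands as a planned activity, and no text places it under 8.2.3.5. Importance is not the same as a positive finding, since an informative null result could qualify. Protocol 8.7 also lets the SAP modify the analysis outline, so a narrower SAP is not in itself a breach. All of this stands. It limits the reach of the clause but does not supply the missing tables. The contents of the adverse reaction listing are not specified, and a listing of cases shows no denominators.

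Three stronger readings are tempting, and the documents support none of them.

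- A reader might infer that selective reporting is now the rule for the study's main question. The unconditional outputs just listed rule that out.
- A reader might infer that the sentence came in when the risk ratios were removed. The amendment log says that some tabulation methods were deleted from 8.2.3.4 and 8.2.3.5, but not whether this sentence was already in version 1.0.
- A reader might put a false-positive rate on the clause. SAP version 2.0 specifies no risk-factor test. The chance that a few cases share a background item by coincidence is the same whatever is reported. The 15% level belongs to the sample-size rationale; SAP 4.1 sets 5%. Even with testing, suppose 2 cases among 40 patients, 12 of whom carry the factor: the smallest Fisher p-value is C(12,2)/C(40,2) = 66/780 = 0.085, so that factor could not reach 5%.

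**Conclusion.** The point holds as a reporting and coverage gap. SAP 8.2.3.5 makes reporting of additional analyses depend on their result, by an undefined standard. For five of the seven risk factors that the SAP names, any ILD comparison would come under that clause, while Protocol 8.7 promises ILD by risk-factor subgroup. This rests on reading an unspecified ILD-by-factor comparison as an additional analysis in the sense of 8.2.3.5; no other analysis section of the SAP covers one. The size is that count of factors. No error rate can be attached to the clause, and neither the sample size nor any planned result changes. It is a cheap improvement.

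**What to change.** Replace the last sentence of SAP 8.2.3.5 with:

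> All exploratory analyses performed will be reported whatever the result, with the number of factors examined; those not specified before database release will be labelled post hoc.

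This alone would not produce a comparison that nobody runs. So also add to SAP 8.2.3.4, before the database release planned for August 2026, simple descriptive ILD counts by the SAP 6.4 factors already collected, reported regardless of result. The missing rows are five factors at two levels each plus age cut at 60: 5 × 2 + 2 = 12 rows, with an unknown row where needed. No tests or risk ratios are called for.

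The cost is one sentence, one short table specification and a slightly longer report. No new data are collected.
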